7.3 Premature Discontinuation

If a participant's participation in the study is terminated prematurely for any reason, the reason for such ET should be documented and the V10 (EOS) procedures should be performed as noted in [Section 7.2.10](#).

A termination form should be completed for every participant who is enrolled, whether the participant completes the study or not. The reason for any ET should be indicated on this form; as much information should be provided as possible. The primary reason for a participant discontinuing early should be selected from the following standard categories of ET:

- *Screen Failure*: Participant does not qualify to participate in the study.
- *Lack of efficacy*
- *Adverse Event*: Clinical or laboratory events occurred that, in the medical judgment of the investigator for the best interest of the participant, are grounds for discontinuation. This includes serious and nonserious AEs regardless of relation to the IMP.
- *Death*: The participant died.
- *Withdrawal of Consent*: The participant desired to withdraw from further participation in the study in the absence of an investigator-determined medical need to withdraw. If the participant gave a reason for withdrawing, it should be recorded.
- *Lost to Follow-up*: The participant stopped coming for visits and study personnel were unable to contact the participant.
- *Non-compliance*: The participant was non-compliant with study visits or procedures.
- *Other*: The participant was discontinued for a reason other than those listed above, such termination of the study by the sponsor.

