The following day, the participants will attend the clinic for the dosing session that will last approximately 6-8 hours and will be supported by two trained therapists. Participants will receive 25 mg COMP360. A full description of the activities of the administration session is found in the Therapist Manual. After the acute effects of COMP360 pass, participants will be evaluated for safety and accompanied home. On the following day, participants will be seen in person for a safety check, assessment of suicidality, and to discuss their experience during the dosing session (integration). During this visit, participants will complete a semi-structured interview on the acceptability of the therapeutic intervention and the severity of PTSD symptoms will be evaluated using the PCL-5. All sessions between the therapists and the participant may be audio recorded for adherence monitoring and quality assurance. Audio and video recording of the sessions are subject to participant consent. Participants who do not consent to either or all recordings will not be excluded from the study.

All participants will be asked to remain off medications for their PTSD symptoms for at least 4 weeks following the administration session. Rescue medications are allowed as noted in the protocol. Participants who restart their medications during the first 4 weeks after the dosing session will be assessed for reasons of resuming their medications and followed until 12 weeks post COMP360 administration. Participants will be seen at the clinic for screening (plus a minimum of 3 safety visits), baseline, day 1, day 2, week 1, week 2, week 4, and week 12 visits. Participants will also be contacted for a remote follow-up at week 6 and week 9. The option of an in clinic visit at weeks 6 and 9 will also be available. See [Section 5.3](#) for a full schedule of assessments. Participants who agreed to the optional neuroimaging component of the study will be offered an MRI scan at week 4.

The study schematic is presented in [Section 5.2](#) and the schedule of assessments is presented in [Section 5.3](#).

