6 POPULATION

6.1 Number of Participants

A total of up to 20 participants will be included with the below eligibility criteria.

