10.1.3 Prohibited Medications

Participants are to be discontinued from antidepressant and/or antipsychotic medications at least two weeks prior to baseline visit. These medications include the following two classes of the Anatomical Therapeutic Chemical (ATC) Classification System: - NO5A Antipsychotics & NO6A Antidepressants. Methylphenidate is also excluded. Participants should also discontinue prazosin one week before COMP360 administration session.

The medical monitor should be contacted if there is any question that a used medication is thought to be in one of these classes. These medications are not to be reintroduced to the participant until after week 4. Participants who require concomitant medication(s) specifically for the treatment of PTSD at any time through the duration of the study will be assessed for reasons of resuming their medications and followed until 12 weeks post COMP360 administration. Participants can resume taking prazosin the day after administration session, if necessary. The study clinician should initiate treatment of symptoms of PTSD as deemed appropriate and may change the venue of therapy (eg outpatient to inpatient) if deemed clinically necessary. The intervention may be a combination of somatic (eg approved antidepressant medication) and non-somatic (various forms psychotherapy, eg TF- CBT) whose therapeutic intention is remediation of PTSD symptoms. Because the anticipated half-life of COMP360 is approximately 3 h, and only 1 administration of test product is permitted, no known issues regarding pharmacokinetics or pharmacodynamic interactions are envisioned within approximately 7 days of product administration.

10.1.4 *Rescue Medication*

Rescue medications may be used during and after the administration session.

The decision to medicate a participant will depend on whether the responsible physician judges that they are capable of maintaining the safety of the participant and others without medical intervention.

- Benzodiazepine anxiolytics is the pharmacological intervention of choice in case of acute psychological distress (eg medications such as lorazepam or alprazolam that have a rapid onset, a short time until peak plasma concentration, and a short duration of therapeutic action; the oral route is preferable because IV injection procedures may further exacerbate the participant's anxiety)

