11.4 Action Taken Regarding Investigational Medicinal Product

Dose modifications of IMP (eg dose not changed, drug withdrawn, drug interrupted, or dose increased) are not applicable as this is a single dose study.

- Not Applicable: Participant died, study treatment had been completed prior to reaction/event, or reaction/event occurred prior to start of treatment

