13 STATISTICS

13.1 Hypotheses and Treatment Comparisons

There are no formal hypotheses being tested in this study.

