13.2 Sample Size Considerations

The sample size is not based on a formal statistical evaluation but is considered to be adequate to meet the objectives of the study.

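### Section 7.3 lets a dosed participant leave for lack of efficacy, an AE or non-compliance without separating this from the end of follow-up, and the SAP labels the early exit assessment Week 12

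*Protocol*

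**What the plan says.** **Reasons for termination.** Protocol 7.3 gives the standard categories for early termination (ET) from the study. Adverse event is described as "Clinical or laboratory events occurred that, in the medical judgment of the investigator for the best interest of the participant, are grounds for discontinuation", whether serious or not and whatever its relation to the drug. Non-compliance is described as "The participant was non-compliant with study visits or procedures". Lack of efficacy is listed without a definition. Section 7.3 also requires the Visit 10 procedures whenever participation ends early. Section 7.2.10 lists these, including C-SSRS, CAPS-5, PCL-5, SDS, EQ-5D-5L and AEs.

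**Single dose.** Section 11.4 says that dose actions "are not applicable as this is a single dose study".

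**Retention.** Section 5.1 says that participants who restart medication in the first 4 weeks are to be "assessed for reasons of resuming their medications and followed until 12 weeks post COMP360 administration". Section 10.1.3 applies the same rule to those who need PTSD medication at any point in the study: they "will be assessed for reasons of resuming their medications and followed until 12 weeks post COMP360 administration".

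**Safety follow-up.** AEs and C-SSRS suicidality are among the primary endpoints (3.1). Known AEs are followed until resolved or stable (12.2), SAEs likewise (12.3), and AESIs to the end of the study (11.10).

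**Analysis.** The CAPS-5 at Weeks 4 and 12 is the last-month version (Protocol 8.1.1). SAP 15.2 gives Visit 10, which is both Week 12 and ET, the single output label Week 12. Absent values are set to missing (SAP 8.1.1), and the C-SSRS is not imputed (SAP 8.3.5). Response and remission are reported both on the FAS total N and on participants with data, n* (SAP 11.1.1).

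**The concern.** The list in 7.3 suits a study with repeated dosing, where stopping treatment and leaving the study are different events. Here the drug exposure is over on Day 1, so leaving afterwards cannot reduce it. What ends is participation, including the scheduled visits that supply the primary safety data and the Week 12 outcomes.

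Two of the categories, adverse event and lack of efficacy, are tied to how the participant is doing, so the missing follow-up may depend on outcome. Safety counts for the later weeks could then omit unobserved events, and a summary headed Week 12 could mix true 12-week scores with scores taken much earlier. A participant who does not improve and needs PTSD medication also falls under two rules: retained to 12 weeks under 10.1.3, yet eligible for termination under 7.3.

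**Working it through.** The plan gives no figure to reproduce. Protocol 13.2 says "The sample size is not based on a formal statistical evaluation but is considered to be adequate to meet the objectives of the study", and no dropout rate is stated. The check is a reading of the sections against each other, with illustrative arithmetic. Inputs from the documents: "A total of up to 20 participants will be included", so N = 20 at most; 12 weeks of follow-up; last-month CAPS-5 recall. The number and timing of exits, the event rates and the responder counts below are assumptions.

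**1. What an exit stops and what continues**

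| Item | After an exit under 7.3 |
|---|---|
| Known AEs, SAEs, AESIs | Still followed (11.10, 12.2, 12.3) |
| New AEs | No scheduled detection; the investigator reports later events judged related or possibly related (11.10, 12.3) |
| C-SSRS | Once at exit, then stops |
| CAPS-5, PCL-5, SDS, EQ-5D-5L | Once at exit, then stop |

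SAP 8.3.1 has an AE onset category for after Week 4 to Week 12. SAP 7 uses the analysis-set N as the default denominator, and SAP 10.1 plans no exposure adjustment. A participant who leaves at Week 2 can therefore count as event-free in weeks that nobody observed.

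**2. Where the sections conflict**

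| 7.3 category | Against 5.1 and 10.1.3 |
|---|---|
| Lack of efficacy, PTSD medication needed | Conflict: may be terminated, but is to be followed to 12 weeks |
| Adverse event | No direct conflict |
| Non-compliance | No direct conflict |

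**3. Person-weeks**

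An exit at Week 2 loses 12 − 2 = 10 of 12 weeks (83%). Total planned: 20 × 12 = 240. For k such exits the share lost is 10k/240:
- k = 1: 10/240 = 4.2%
- k = 2: 20/240 = 8.3%
- k = 4: 40/240 = 16.7%

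**4. Chance of seeing at least one late event, 1 − (1 − p)^n**
- p = 5%: 64.2% with n = 20, 56.0% with n = 16
- p = 10%: 87.8% with n = 20, 81.5% with n = 16

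**5. If the ET score is reported as Week 12, as the label implies**

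Taking last month as 30 days, the share of the recall window before dosing, for an exit d days after the dose, is (30 − d)/30:
- d = 7: 23/30 = 77%
- d = 14: 16/30 = 53%
- d = 28: 2/30 = 7%

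A window that is partly pre-dose would tend to understate improvement. A participant who would later have worsened is instead fixed at an earlier, better score. The net direction is unknown.

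**6. If the ET score is left out of Week 12**

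With 10 responders and k non-responders leaving, the response proportion is 10/(20 − k) on n* and 10/20 on N:

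| k | n* | N |
|---|---|---|
| 0 | 50.0% | 50.0% |
| 1 | 52.6% | 50.0% |
| 2 | 55.6% | 50.0% |
| 4 | 62.5% (Wald 95% CI 38.8 to 86.2) | 50.0% (28.1 to 71.9) |

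For mean CAPS-5 change, assume −18 in stayers and −2 in leavers. The observed mean is −18. The mean over all 20 is (19 × −18 − 2)/20 = −17.2 for k = 1, and (16 × −18 − 8)/20 = −14.8 for k = 4. The N denominator protects the response proportion from this inflation; nothing protects the mean.

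**The case against.** The strongest answer is that 7.3 is mainly a list for coding the primary reason on a form. It directs nobody to terminate anyone, and it also covers screening and taper, where exits for an AE or non-compliance make sense. This stands in part. However, the AE category rests on the investigator's judgment, and withdrawal of consent is listed separately, so exit at the investigator's decision after dosing is allowed for.

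A reader might infer three stronger things that the documents do not support:

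- **That Week 12 safety and outcome data are simply lost.** Sections 7.3 and 7.2.10 require the full Visit 10 set at any early exit, and known events are still followed. The gap is scheduled C-SSRS, detection of new AEs, and true 12-week status.
- **That an exit can end nothing but observation.** Integration sessions run to Week 2, participants are asked to stay off PTSD medication until after Week 4, and some have optional blood draws and an MRI scan. Leaving spares these burdens, so the investigator's judgment about them has a purpose.
- **That all three categories contradict 5.1 and 10.1.3.** Those sections cover only participants who restart or need PTSD medication.

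It is also fair to say that the study is small and descriptive: "There are no formal hypotheses being tested in this study". That lowers the stakes for efficacy, but safety through Week 12 is the primary objective.

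**Conclusion.** The point holds in a limited form. Section 7.3 allows a dosed participant to be taken out of scheduled follow-up for an undefined lack of efficacy, an AE or non-compliance, and nothing in the protocol separates these events from the end of follow-up. The consequences are incomplete primary safety data after exit, and an exit assessment that carries the Week 12 label whatever its timing. For participants who need PTSD medication, termination for lack of efficacy conflicts with 5.1 and 10.1.3, and these passages must be reconciled.

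The size is not known. The 4% to 17% of person-weeks rests on 1 to 4 exits, all at Week 2, among 20 participants, and the response and mean-change figures rest on assumed outcomes. It would be tempting to conclude that the results will look too safe and too effective. For efficacy that does not follow: the direction depends on whether exit scores enter the Week 12 summary, and response and remission are also reported on N. Nor do the documents show that leavers would all be the highest-risk participants, least of all those leaving for non-compliance.

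One limit applies. The SAP is based on protocol V5.0, while the protocol reviewed here lacks items in the SAP such as BPRS+, EBI and the Cue app. It may be an earlier version, so 7.3 should be checked in V5.0.

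**What to change.** **Protocol 7.3.** For dosed participants, record lack of efficacy, AE and non-compliance as dated events. State that these do not by themselves end the scheduled AE, C-SSRS, PCL-5 and CAPS-5 follow-up to Week 12, done remotely where feasible, while the participant consents and can be reached. State also that the investigator's judgment on care and on other study procedures is unchanged. Define lack of efficacy or remove it as a reason for ending follow-up, and reconcile it with 5.1 and 10.1.3. Keep the current categories for exits before dosing.

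**SAP 15.2.** Assign ET assessments by actual time since dose, and do not report them automatically as Week 12.

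**Cost.** One protocol paragraph and one SAP sentence. The visits are already scheduled, and Weeks 6 and 9 can already be remote. The downside is some effort to retain participants. The SAP addendum was written after database lock; if no further data can be collected, the SAP change can still be made, and the report can give the number, reason and timing of exits after dosing.

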8 DESCRIPTION OF STUDY PROCEDURES

8.1 Efficacy Assessments

8.1.1 *Clinician-Administered PTSD Scale for DSM-5*

The CAPS-5 is the gold standard clinician rated assessment for PTSD. It consists of 30 items and can be used for diagnostic purposes as well as monitoring PTSD symptoms severity over time. Each item could be rated as 0=absent, 1=mild/subthreshold, 2=moderate/subthreshold, severe/markedly elevated, 4=extreme/ incapacitating. At baseline visit the last month version of CAPS-5 will be used for diagnostic purposes. The last month version of the assessment will be administered to monitor participant symptoms improvement after treatment at weeks 4 and 12.¹³

8.1.2 *EuroQoL-5-dimension 5-level Scale*

The EQ- 5D- 5L was introduced by the EuroQoL Group in 2009.^{21,22} The EQ-5D-5L consists of 2 sections: the EQ-5D-5L descriptive system and the EQ visual analogue scale (EQ VAS).

The descriptive system comprises five dimensions: mobility, self-care, usual activities, pain/discomfort, and anxiety/depression. Each dimension has five levels: no problems, slight problems, moderate problems, severe problems and extreme problems. The participant is asked to indicate his/her health state by ticking the box next to the most appropriate statement in each of the five dimensions. This decision results in a 1-digit number that expresses the level selected for that dimension. The digits for the five dimensions can be combined into a 5-digit number that describes the participant's health state.

The EQ VAS records the participant's self-rated health on a vertical VAS, where the endpoints are labelled 'The best imaginable health state' and 'The worst imaginable health state'. The VAS can be used as a quantitative measure of health outcome that reflect the participant's own judgement.

The EQ-5D-5L will be obtained at baseline, week 4, and week 12 visits.

8.1.3 *Sheehan Disability Scale*

The SDS is a brief, 5-item inventory that assesses functional impairment in work/school, social life, and family life. The total score ranges from 0 to 30 with 0 representing no impairment and 30 representing severe impairment. The last two items of the scale (Days Lost and Days Unproductive) do not count toward the total score. Each domain is rated on a 10-point visual analogue scale (VAS).¹⁴ The SDS will be completed by participants at baseline, week 4 and week 12.

8.1.4 *Resilience Adult Scale*

The RAS was developed to capture a set of fundamental protective factors based on resilience research. It includes 33 items, in a six-factors structure including (1) perception of self, (2)

planned future, (3) social competence, (4) structured style, (5) family cohesion, (6) social recourses.¹⁵

8.1.5 *Perceived Ability to Cope with Trauma Scale*

The PACT scale is a self-reported, 20 items scale, organised in two sub-scales, (1) Forward focus and (2) Trauma focus. The first subscale measures the ability of the individual to move beyond their trauma, while the second measures the perceived ability to focus on processing the trauma. Overall the scales provides a quantification of the individual's coping flexibility.¹⁶

8.2 Safety Assessments

8.2.1 *Columbia-Suicide Severity Rating Scale*

The C-SSRS will be used to assess suicide potential or tendency as a study entry criterion and monitored throughout the study.

The C-SSRS is a semi-structured interview designed to assess the severity and intensity of suicidal ideation, suicidal behaviour, and non-suicidal self-injurious behaviour over a specified time period. The measurement of suicidal ideation is based on five “yes” or “no” questions with accompanying descriptions arranged in order of increasing severity. If the patient answers “yes” to either questions 1 or 2, the intensity of ideation is assessed in five additional questions related to frequency, duration, controllability, deterrents, and reasons for the most severe suicidal ideation. Suicidal behaviour is assessed by asking questions categorising behaviours into actual, aborted, and interrupted attempts; preparatory behaviour; and non-suicidal self-injurious behaviour.

If any item(s) on the C-SSRS are answered “yes”, the primary investigator or physician investigator must review the patient's responses in order to (a) at screening and day-1 determine the patient's study eligibility and potential need for referral to a mental health professional, and (b) during the study evaluate the patient's need for appropriate medical management such as a referral to a mental health professional.

A significant risk of suicide is defined as a “yes” in answer to (a) questions 4 or 5 on the suicidal ideation section; or (b) any questions on any item in the suicidal behaviour section. This must be reported as an AE or SAE as appropriate and followed up accordingly. Additionally, if a patient responds “yes” to any of the suicidal ideation questions 1 through 3, the investigator should apply clinical judgment to determine the need for reporting this as an AE or SAE and the need for any appropriate referral.

The C-SSRS will be collected at every visit.

8.2.2 *Vital Signs*

Blood pressure will be measured sitting, after at least 5 min at rest. The three measurements should be recorded 1 to 2 min apart, and the results averaged to inform eligibility at screening and baseline. Blood pressure, body temperature, and pulse rate will be obtained at screening, baseline, and day 2.

8.2.3 *Electrocardiogram*

Standard 12-lead ECGs will be obtained at screening, baseline, and day 2.

8.2.4 *Clinical Laboratory Tests*

Clinical laboratory evaluations will be performed including blood chemistry, haematology, urinalysis, urine drug screen, and urine pregnancy test (for women of childbearing potential). Blood samples for clinical laboratory tests will be collected at screening, baseline, and day 2. Urine samples will be collected at screening and baseline. The details of the analyses are listed in Table 8.1. and in the Schedule of Assessments in Section 5.3.

Table 8.1 List of clinical laboratory evaluations

Haematology	Chemistry
Haemoglobin	Albumin
Haematocrit	Alkaline phosphatase
Red blood cell count	Alanine aminotransferase (ALT)
Mean corpuscular haemoglobin	Amylase
Mean corpuscular volume	Aspartate aminotransferase (AST)
Mean corpuscular haemoglobin concentration	Bicarbonate
White blood cell count (with differential)	Bilirubin (direct, indirect, and total)
Platelet count	Calcium
	Chloride
	Creatine kinase
	Creatinine
	Gamma-glutamyl transferase
	Glucose
	Lactate dehydrogenase
	Lipase
	Magnesium
	Phosphate
	Potassium
	Protein-total
	Sodium
	Urea (blood urea nitrogen)
	Uric acid
Urinalysis (dipstick)	Urine Drug screen
Blood	Amphetamines
Glucose	Barbiturates
Ketone	Benzodiazepines
Protein	Cocaine
pH	Cannabinoids
Specific gravity	Opiates
Nitrite	
Leukocytes	
Bilirubin	
Urobilinogen	
Others	
Urine pregnancy dipstick	

8.2.5 *Adverse Events*

All AEs occurring after the participant signs the ICF and up to the last study event will be recorded. Any AEs occurring before the start of treatment (eg, before the dose of the IMP on day 1) will be recorded as pre-treatment AEs. Any SAE ongoing at V12 (EOS/ET) will be followed until resolution or no longer considered clinically significant.

See [Sections 11](#) and [12](#) for additional information.

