The baseline visit should occur within 3 to 6 weeks after initial screening. At baseline visit, the participant's eligibility will be confirmed by reviewing the Inclusion/Exclusion Criteria (Sections 6.2 and 6.3) and updating medical history.

The following procedures will be performed and recorded at this visit:

- C-SSRS (Since Last Visit)
- CAPS-5
- EQ-5D-5L

- SDS
- RAS
- PACT
- Semi-structured PTSD management interview
- Vital signs (ie supine, after at least five mins of rest, diastolic and systolic blood pressure, pulse, and body temperature)
- Blood and urine samples for:
 - Clinical laboratory tests
 - Biomarkers, if the participant opts to participate in this part of the study
 - Urine drug screen
 - Urine pregnancy test for all women of childbearing potential
- Medications taken and any changes in medications since the previous visit
- AEs and Serious AEs (SAEs) ([Sections 11 and 12](#))

If the participant continued to meet the eligibility criteria, the trained therapist will review psychoeducational material and the anticipated psilocybin session with the participant. If the participant remains eligible, arrangements will be made for the participant to return to the study site for IMP administration the next day. After baseline data is entered into EDC, the CAT team will complete a final review to ensure the participant's continued eligibility. Participants cannot be progressed to the administration session until this approval is received.

If the participant opts to participate in the neuroimaging part of the study, specific eligibility criteria will be reviewed by the investigator ([Section 6](#)). If considered eligible, the participant will undergo an MRI scan.

7.2.3 *Visit 3 – Day 1 – Administration Session*

The administration session should occur the day after baseline visit. During this session (the day of COMP360 administration), the following are to be obtained:

- Vital signs (ie supine after at least five mins of rest diastolic and systolic blood pressure, pulse, body temperature, and respiratory rate). Before dosing
- Administration of study drug ([Section 9.3](#)). The dosing session may be video recorded for training and adherence monitoring. A full description of the activities of the dosing session is found in the Therapist Manual. After approximately 6-8 h, participants will

be assessed for safety and to ensure the acute drug effects have subsided before being accompanied home.

- C-SSRS (Since Last Visit), after dosing

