- Medications taken and any changes in medications since the previous visit
- AEs and SAEs ([Sections 11](#) and [12](#)) after dosing

7.2.4 *Visit 4 – Day 2*

On the day following IMP administration, the participant will return to the study site for a safety check and to discuss their experience during the administration session. The following will be obtained at this visit:

- C-SSRS (Since Last Visit)
- PCL-5
- Vital signs (ie, supine, after at least five mins of rest, diastolic and systolic blood pressure, pulse, and body temperature)
- 12-lead ECG
- Blood samples for clinical laboratory tests
- Medications taken and any changes in medications since the previous visit
- AE and SAE ([Sections 11](#) and [12](#))
- Semi-structured qualitative interview
- Integration session with the trained therapist

Participants will be asked to remain off medications for PTSD until after week 4.

7.2.5 *Visit 5 – 1 Week Post-administration*

The participant will visit the clinic 1 week (\pm 1 day) following study drug administration; the following assessments will be obtained at this visit:

- C-SSRS (Since Last Visit)
- PCL-5
- Medications taken and any changes in medications since the previous visit
- AE and SAE ([Sections 11](#) and [12](#))
- Integration session with the trained therapist

Participants will be reminded to remain off medications for PTSD until after week 4.

7.2.6 *Visit 6- 2 Weeks Post-administration*

The participant will visit the clinic 2 weeks (\pm 1 day) following study drug administration; the following assessments will be obtained at this visit:

- C-SSRS (Since Last Visit)
- PCL-5
- Medications taken and any changes in medications since the previous visit
- AE and SAE ([Sections 11 and 12](#))
- Integration session with the trained therapist

Participants will be reminded to remain off medications for PTSD until after week 4.

7.2.7 *Visit 7- 4 Weeks Post-administration*

The participant will visit the clinic 4 weeks (\pm 1 day) following study drug administration; the following assessments will be obtained at this visit:

- C-SSRS (Since Last Visit)
- CAPS-5
- PCL-5
- EQ-5D-5L
- SDS
- RAS
- PACT
- Blood samples for:
 - Biomarkers, if the participant opts to participate in this part of the study
- Medications taken and any changes in medications since the previous visit
- AE and SAE ([Sections 11 and 12](#))

If the participant opts to participate in the neuroimaging part of the study, they will undergo an MRI scan.

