⁵ Body temperature and respiratory rate will be measured before and at the end of the COMP360 administration session. Blood pressure and pulse rate measurements will be collected via an automatic arm cuff, with measurements collected supine at rest, in triplicate approximately one minute apart, at 15 minutes before COMP360 administration, and at one hour, three hours and six hours after

COMP360 administration. Measurements should be collected within a ± 10 -minute time window. At the end of the COMP360 administration session, a final triplicate measurement will be taken after the participant has rested for at least five minutes in the sitting position.

⁶ See protocol Section 8.2.4 for complete list of required tests to be performed.

⁷ For women of child-bearing potential only.

⁸ Only clinical laboratory tests will be tested at this visit.

⁹ Optional components of the study.

¹⁰ Baseline MRI scan can be completed within ≤ 7 days prior to baseline visit.

¹¹ Participants will have two preparation sessions during the screening period and one on day -1.

¹² Psychoeducational information will be provided by the therapist during the preparation sessions in the screening period.

¹³ Collection starting from V1b through to Baseline for those participants requiring withdrawal from prohibited medications.

¹⁴ The EBI must be performed after integration on day 2.

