15.4 Baseline Definitions

Table 17: Baseline Definitions

Parameter	Baseline
Safety	
All	Day -1
Vital Signs	Day 1 (pre-COMP360 administration)
Efficacy	
All	Day -1

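### Protocol 8.2.2 asks for sitting blood pressure where the visit sections ask for supine, so the Day 2 change from a supine pre-dose baseline, and the eligibility reading, can mix postures

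*Protocol*

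**What the plan says.** Protocol 8.2.2 (Vital Signs) gives a posture, "Blood pressure will be measured sitting, after at least 5 min at rest", has three measurements averaged to inform eligibility at screening and baseline, and names the visits: "Blood pressure, body temperature, and pulse rate will be obtained at screening, baseline, and day 2".

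The visit-by-visit text gives another posture. Sections 7.2.1 (screening) and 7.2.4 (Day 2) both list "Vital signs (ie, supine, after at least five mins of rest, diastolic and systolic blood pressure, pulse, and body temperature". Section 7.2.2 (baseline, Day -1) lists "Vital signs (ie supine, after at least five mins of rest, diastolic and systolic blood pressure, pulse, and body temperature". Section 7.2.3 (Day 1) lists "Vital signs (ie supine after at least five mins of rest diastolic and systolic blood pressure, pulse, body temperature, and respiratory rate). Before dosing".

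In the SAP, footnote 5 to Table 2 describes Day 1 blood pressure and pulse before dosing and at 1, 3 and 6 h, "with measurements collected supine at rest, in triplicate approximately one minute apart". For the end of the session it adds that "a final triplicate measurement will be taken after the participant has rested for at least five minutes in the sitting position". SAP 8.3.3 repeats the supine series, does not mention the sitting reading, and gives no posture for screening, baseline or Day 2.

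SAP Table 17 sets the vital signs baseline as "Day 1 (pre-COMP360 administration". SAP 10.3 summarises change from baseline on both non-administration and administration visits, and by timepoint on Day 1. Vital signs are listed among the primary endpoints in both documents.

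**The concern.** A site cannot take one reading both sitting and supine. With two instructions for the same visit and no rule of precedence, sites may differ from each other, or one site may differ between visits. The Day 1 pre-dose reading that serves as baseline is supine under both documents, so a sitting Day 2 reading would be compared with a supine one. Any posture difference would then appear in the reported Day 2 change in a primary safety measure, and there is no control arm in which the same shift would show.

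The conflict also reaches entry to the study. The exclusion for hypertension is set at blood pressure above 140/90 mmHg, 8.2.2 says averaged readings inform eligibility, and the posture of those readings is given two ways.

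**Working it through.** The plan states no figure for this point, so the check sets the passages side by side and follows each planned comparison.

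**Posture by reading**

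| Reading | Protocol 8.2.2 | Protocol visit section | SAP |
|---|---|---|---|
| Screening | sitting | supine (7.2.1) | none given |
| Baseline, Day -1 | sitting | supine (7.2.2) | none given |
| Day 1 pre-dose | not in its visit list | supine (7.2.3) | supine |
| Day 1 at 1, 3, 6 h | not in its visit list | not scheduled | supine |
| Day 1 end of session | not in its visit list | not scheduled | sitting (footnote 5 only) |
| Day 2 | sitting | supine (7.2.4) | none given |

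The protocol's schedule of assessments gives no posture. SAP section 1 lets the SAP override the protocol on statistical analysis, which does not cover how a reading is taken. The post-lock SAP addendum does not touch vital signs.

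**Planned comparisons**

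1. Day 1 pre-dose to 1, 3 and 6 h: supine to supine. Consistent.
2. Day 1 pre-dose to Day 2: supine to supine if the site follows 7.2.4, supine to sitting if it follows 8.2.2. Both kinds of pair would be pooled in SAP Table 14.3.5.1.
3. Day 1 pre-dose to end of session: the later reading is sitting under footnote 5. The Day 1 labels in SAP Table 16 stop at 6 hours, and Day 1 summaries are by timepoint, so the SAP does not settle whether this reading enters a change summary.
4. Eligibility at screening and baseline: sitting under 8.2.2, supine under 7.2.1 and 7.2.2.

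**How a posture difference would carry through**

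Let d be the mean sitting-minus-supine difference, which the documents do not give. Suppose k of n participants have a sitting Day 2 reading against a supine baseline. The mean Day 2 change then moves by (k/n) × d. If all 20 planned participants contribute, each mismatched pair moves the mean by d/20 = 0.05d, ten pairs by 10/20 × d = 0.5d, and twenty by d. Neither k nor d can be obtained from the documents.

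**Counts outside limits**

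The counts outside 90/160 mmHg systolic and 50/100 mmHg diastolic compare observed values with fixed limits. Baseline does not enter them. A posture shift at the visit changes a participant's status only if the reading lies within that shift of a limit.

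**The case against.** The strongest reply is that the comparison that matters most is sound. The documents put the psilocin half-life at about 3 h and have the effects subsiding after 5 to 6 h. The supine series at 1, 3 and 6 h covers that window against a supine baseline, while Day 2 falls about a day after dosing. This stands, and it confines the point to Day 2, the end-of-session reading and eligibility.

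The version objection also stands. The SAP rests on UK and US protocols V5.0. The supplied protocol appears to be another version: it has no BPRS+, EBI, 5D-ASC or mDESS, names a different phone app, and takes Day 1 vital signs only before dosing. Linking its 8.2.2 to the SAP baseline assumes that 8.2.2 did not change. The conflict within the supplied protocol and the two postures in SAP footnote 5 need no such link.

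A reader might infer that posture and drug effect cannot be told apart. That goes too far. Observed values are summarised by visit and all data are listed. At a site that applied one instruction throughout, Day -1 to Day 2 is a same-posture check. It helps only where practice was consistent, and the SAP does not plan it as a change summary.

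A reader might also infer that every end-of-session reading is compared with a baseline in another posture. With no timepoint label, the documents do not establish that.

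**Conclusion.** The contradiction is real and lies within the supplied protocol. Following the plan as written can pool sitting-to-supine with supine-to-supine pairs in the Day 2 change in blood pressure, and leaves the posture behind the 140/90 mmHg exclusion unsettled. The link to the SAP's Day 2 change is conditional on 8.2.2 being the same in V5.0 and on some sites having followed it. The handling of the sitting end-of-session reading is undefined.

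No size is asserted. It would be tempting to assume a posture difference and express it in standard errors. That would require every participant to be mismatched in the same direction, and it would match no planned output: SAP section 7 plans n, mean, SD, median, minimum and maximum for continuous data, and the SAP's confidence intervals belong to efficacy. Nor do the documents support a one-for-one effect on the counts outside limits, which could shift only for readings near a limit.

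**What to change.** - **Protocol.** Reconcile 7.2.1 to 7.2.4 with 8.2.2 so that one posture applies at screening, baseline, Day 1 pre-dose and Day 2, including the averaged reading used for eligibility. Which posture that is should be the sponsor's decision. Check first whether V5.0 already does this.
- **SAP.** Compute change from baseline in blood pressure only from same-posture pairs. Give the end-of-session sitting reading its own label in Table 16 and show it as an observed value only.
- **Data already collected.** The SAP addendum was written after database lock, so a new CRF field would not recover posture. Use posture from source where it was recorded. Where it was not, show the Day -1 to Day 2 change alongside the planned Day 2 change and disclose the ambiguity in the CSR.

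The cost is small wording and programming changes, with no extra measurement on participants. The downside is possibly fewer Day 2 pairs in the change summary.
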